##### Statistical model for estimating the inter-participants (intra participants for test and reference) variability for PK parameters – AUC (0-30min), AUC (0-∞), Cmax and AUC (0-last)

For each cohort, following  $\log_e$ -transformation, AUC (0-30min.), AUC (0-∞), Cmax and AUC (0-last) will be analyzed using a mixed effect model approach with fixed for period, treatment group and treatment group as random effects. Factor Analytic (FA(02)) variance and covariance structures will be assumed. If the above model fails to converge, other covariance structures (e.g. UN, CS, AR(1), VC etc.) might be investigated. SD in  $\log_e$  scale and coefficient of variance (CV) for inter-participants will be calculated.

- Total participants variability will be calculated as the sum of intra (within)- participants and inter-participants variability.

If an intercurrent events (ICEs) (as described in Section 4.3.1.1 - intra-participants variability of PK parameters) happens during a specific treatment period, and this event affects the measurement of individual pharmacokinetic (PK) concentrations (pharmacokinetic data), then the data points for those affected individuals in the treatment period will be set to missing.

Graphs for Pharmacokinetic (PK) parameters -

- Individual plasma concentration - time plots (linear and semi-logarithmic) by subjects
- Individual plasma concentration - time plots (linear and semi-logarithmic) by treatment group
- Median (range) plasma concentration - time plot (linear and semi-logarithmic) by treatment group
- Mean ( $\pm$  SD) plasma concentration - time plots (linear and semi-logarithmic) by treatment group
- Mean ( $\pm$  SD) plasma concentration - time plots (linear and semi-logarithmic)

To present the descriptive statistics and plots for PK parameters, refer the GSK statistical analysis SOPs.

Listing for PK concentration and PK parameters (AUC(0-30min), AUC(0- $\infty$ ), Cmax, Tmax, t1/2 and AUC(0-last)) will be generated using PK analysis set.

#### 4.3.2. Handling missing data of PK parameters

CCI

CCI (refer protocol Section 8.5 for detailed information). Refer GSK statistical analysis SOPs for the rules of handling missing PK parameters data and below LLOQ value.

Outliers - Any participants excluded from the summaries and/or statistical analyses will be documented along with the reason for exclusion in the clinical study report.

#### 4.4. Exploratory Endpoint(s) Analyses

The exploratory pharmacodynamics (PD) endpoints are -

- Minimum serum potassium
- MHR
- Maximum QTc interval

The exploratory pharmacodynamics (PD) endpoints will be analyzed for Cohort 1 and Cohort 2 using FAS. All PD parameters will be summarized by study treatment.

Statistical model for the analysis of exploratory PD endpoints in each cohort

Following loge-transformation, minimum serum potassium, MHR and maximum QTcF interval will be analyzed using mixed effect model approach with fixed effect for period, treatment group. The point estimates and their associated 90% CI will then be back-transformed to provide point estimates and 90% CI for the ratios (GMR) of HFA-152a MDI (test)/HFA-134a MDI (reference).

For the untransformed data of pharmacodynamics (PD) parameters (minimum serum potassium, MHR (Maximum HR, maximum QTc interval)), descriptive statistics (N, n, AM, 95% CI of AM, SD) median, minimum and maximum) will be computed for FAS.

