4. STUDY DESIGN

4.1. Overall design

This is a randomized, open-label, single dose, 2-sequence, 2-treatment arm, 4-way cross-over (2x2x4) single-center study in healthy participants aged 18 to 55 years. Salbutamol will be administered as either a 200 µg or 800 µg dose, given as 2 or 8 actuations respectively at 20 second intervals, each delivering 100 µg as the ex-valve dose of HFA-152a or HFA-134a. Sequential enrollment approach will be followed for the study. Participants in Cohort 2 will be enrolled once participants in Cohort 1 have completed the study. An interim analysis is planned for when last participant enrolled for the 200 µg (Cohort 1) completes their last visit, and final analysis will be conducted when the last participant of 800 µg (Cohort 2) completes their last visit.

The study has planned to enroll a total of 60 participants to either Cohort 1 (200 µg) or Cohort 2 (800 µg) to ensure at least 56 participants in the PK analysis set (see Section 9 on analysis sets). For each cohort, 30 healthy participants will be randomly assigned to a cohort to ensure at least 28 participants are included in the PK analysis set with 15 randomized to each treatment sequence.

Following treatment sequences will be applied in each cohort:

Treatment Sequence 1: TRRT

Treatment Sequence 2: RTTR

Where T is salbutamol HFA-152a (test) and R is salbutamol HFA-134a (reference).

In Cohort 1, salbutamol will be administered as single 200 µg dose, given as 2 actuations each separated by a 20-second interval, each delivering 100 µg of salbutamol (as salbutamol sulfate) as the ex-valve dose for the HFA-152a MDI or HFA-134a MDI.

In Cohort 2, salbutamol will be administered as single 800 µg dose, given as 8 actuations each separated by a 20-second interval, each delivering 100 µg of salbutamol (as salbutamol sulfate) as the ex-valve dose for the HFA-152a MDI or HFA-134a MDI.

Participants will attend a screening visit between Day-28 and Day-1. The intervention period will be 10 days with dosing on Day 1, Day 4, Day 7, and Day 10. Participants will be discharged on Day 11. There will be a follow-up period between Day 12 and Day 18.

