9.3.2. Tertiary/exploratory endpoint(s) analysis

9.3.2.1. Pharmacodynamic analysis

For each cohort, the following PD parameters will be evaluated and compared between Salbutamol HFA-152a MDI (test) and Salbutamol HFA-134a MDI (reference): minimum serum potassium, MHR and maximum QTcF interval.

Following log_e-transformation, minimum serum potassium, MHR and maximum QTcF interval will be analyzed using mixed effect model approach with fixed effect for period, treatment group and participants as random effects. The point estimates and their associated 90% CI will then be back-transformed to provide point estimates and 90% CI for the ratios (GMR) of HFA-152a MDI (test)/HFA-134a MDI (reference).

The exploratory PD parameters data will be summarized using descriptive statistics (N, n, AM, GM, SD, SD in log scale CV %, median, minimum, and maximum), and will be summarized in tabular and/or graphical form.

CCI

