## VERSION HISTORY

SAP Version	Approval Date	Protocol Version (Date) on which SAP is Based	Change	Rationale
SAP	20 May 2024	1.0 (18 Jan 2024)	Not Applicable	Original version
SAP Amendment 1	25 Sep 2024	- Protocol Amendment 1 (02 May 2024)	
 
- Sensitivity Analysis for PK parameters as per FDA and EMA regulatory guideline
 
- Random effect has been removed from linear mixed model for analyzing the exploratory PD endpoints
 
	
 
- If <math>SWR \geq 0.294</math> for <math>C_{max}</math>, <math>AUC(0-\infty)</math> and <math>AUC(0-last)</math> then Reference Scale Average Bioequivalence (RSABE) will be used to analyse the PK parameters.
 
- Based on derivation of PD parameters, each participant will have single observation for the study therefore random effect is not required while estimating the PD parameters.
 

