##### Statistical model for the analysis of primary PK parameters - AUC(0-30min), AUC(0- $\infty$ ) and Cmax

For each cohort, following  $\log_e$ -transformation, AUC(0-30min.), AUC(0- $\infty$ ) and Cmax will be separately analyzed using mixed effect model approach with fixed effect terms for sequence, period and treatment group. Participants will be treated as random effects in the model. Factor analytic (FA(02))variance and covariance structures will be assumed. If the above model fails to converge, other covariance structures (e.g., UN, CS, AR (1), VC etc.) might be investigated. The point estimates and their associated 90% CI will then be back-transformed to provide point estimates and 90% CI for the ratios (GMR) of HFA-152a MDI (test)/HFA-134a MDI (reference).

If an intercurrent event (ICE) (as described in Section 1.1) happens during a specific treatment period, and this event affects the measurement of individual pharmacokinetic (PK) concentrations (pharmacokinetic data), then the data points for those affected individuals in the treatment period will be set to missing.

[figure not shown]

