#### 4.5.3.3. ECG

The arithmetic mean of the three recorded 12-lead ECGs measurements will be presented in all data summaries of 12-lead ECGs measurements at predose and single measurement of post dose for days 1, 4, 7 and 10 and discharge. ECG measurements will be recorded, including heart rate (HR), PR interval, QRS duration, QT interval, and RR interval. QT intervals will be based on Fridericia's formula and reported as per captured in eCRF:

Descriptive statistics (n, mean, standard deviation (SD), median, minimum value (min), and maximum value (max)) will be presented at baseline, and absolute and change from baseline for HR, QTc and other ECG parameters at each assessed visit for on-treatment period for Safety analysis set.

As per protocol SOA Section 1.3, safety ECG data are not collected for follow up visit, therefore on-treatment period will be same as overall period.

Participants listings will be provided for all 12 lead ECGs values and findings including abnormal ECGs for each treatment sequence and period in Safety analysis set.

[figure not shown]

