#### **6.2.2. Study Period**

Assessments and events will be classified within each cohort according to the time of occurrence relative to the study treatment period (days).

**Pre-Treatment:** For the presentation of serious adverse events (SAEs), concomitant medications, and other assessments in pre-treatment is defined as -

Date of assessment < Study treatment start date of period 1 (day 1).

**On-Treatment:** For the presentation of adverse events (AEs), serious adverse events (SAEs), concomitant medications, 12-lead ECG, vital signs, and other assessments in on-treatment is defined as -

Study treatment start date of period 1 (day 1) <= Date of assessment <= Study treatment stop date of period 4 (Day 10) or early withdrawal + 1 day

Worsening in AE (change in AE severity from lower severity to higher severity category) relative to the pre-study treatment state will also be considered as on-treatment AE.

If time of assessment or study treatment is not collected (missed), the following assessment on the first dose date will be assumed to be taken prior to the first dose and therefore considered pre-treatment.

As per study design, Four Treatment Periods of the study are defined below.

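### SAP 4.4 removes the participant random effect from the PD model for a reason that does not fit the four-period crossover

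*SAP*

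**What the plan says.** Protocol 9.3.2.1 has log-transformed minimum serum potassium, maximum heart rate and maximum QTcF "analyzed using mixed effect model approach with fixed effect for period, treatment group and participants as random effects". SAP 4.4 keeps the mixed-model label, but the same endpoints "will be analyzed using mixed effect model approach with fixed effect for period, treatment group". No random term and no residual covariance structure is named. The output is a back-transformed test/reference ratio with a 90% CI, and "All PD parameters will be summarized by study treatment".

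The change is declared. The SAP version history for Amendment 1 refers to the derivation of the PD parameters and says that "each participant will have single observation for the study therefore random effect is not required while estimating the PD parameters".

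For the PK endpoints of the same design, the primary model in SAP 4.2.2 adds sequence, says "Participants will be treated as random effects in the model" and names a covariance structure.

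**The concern.** A participant effect can be dropped without loss only if each participant contributes one value. The visible design points the other way:

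- Protocol 4.1 has "dosing on Day 1, Day 4, Day 7, and Day 10", in sequence TRRT or RTTR, so each person receives each product twice.
- Protocol 1.3 (footnotes g and i) schedules potassium samples and ECGs on all four dosing days, and identifies QTc and heart rate from the ECG as PD parameters.
- SAP 4.5.3.3 presents ECG data "at predose and single measurement of post dose for days 1, 4, 7 and 10 and discharge".
- SAP Table 1 sets a separate baseline for potassium and ECG in each period, and SAP 6.2.2 says "As per study design, Four Treatment Periods of the study are defined below".
- A study-wide single value has no natural period or treatment, yet SAP 4.4 fits both.

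Hypokalaemia and cardiovascular effects are the risks that protocol 2.3.1 lists should the new propellant deliver more salbutamol. SAP 4.4 holds the only modelled test/reference comparison of those effects. The safety ECG and laboratory outputs are descriptive. A model that ignores the pairing gives up the precision that protocol 4.2 cites as the reason for a crossover. On one reading it also shrinks a real difference.

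**Working it through.** **The plan's own precision figure.** None is stated for PD. The PK figure (protocol 9.5, SAP 5) is a half-width of 16.44% for n = 28 and CVw = 50%. Within-participant SD = sqrt(ln(1 + 0.50²)) = 0.4724. SE = 0.4724/sqrt(28) = 0.0893. With t(0.95, 26 df), exp(t × SE) - 1 = 16.45%, which reproduces it. This precision uses within-participant error only, and that is what the PD model as written gives up.

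**Inputs.** 28 participants (the PK-set target), 14 per sequence, four dosing days, log scale, within-participant SD set to 1. The documents give no PD variance components, so ICC is an assumption shown over a range. The number of PD values per participant entering the model is not in the visible text, so three readings were worked through.

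**Reading A: one value per period.** There are 28 × 4 = 112 values. In complete TRRT/RTTR data the treatment contrast lies within participants, with variance σw²/28. A model without a participant term uses σw² + σb² in place of σw². The point estimate is identical, and the interval is too wide by

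sqrt((σw² + σb²)/σw²) = 1/sqrt(1 - ICC).

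This assumes independent residuals and no participant-by-treatment interaction. Residual df are 112 - 5 = 107 without the participant term and 107 - 27 = 80 with it. Simulation used 20,000 trials per ICC.

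**Reading B: one extreme per treatment.** Two values per participant are compared as if unpaired (54 df) rather than paired (27 df). The maximum of two replicates has within-participant variance (1 - 1/π)σw² = 0.682σw², so the factor is about sqrt(1 + [ICC/(1 - ICC)]/0.682) = 1.17, 1.57 and 2.62 at ICC 0.2, 0.5 and 0.8. The different t quantiles lower this slightly. Simulation used 10,000 trials per ICC. A period term is not defined on this reading.

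| Reading | Quantity | ICC 0.2 | ICC 0.5 | ICC 0.8 |
|---|---|---|---|---|
| A | Width ratio, without/with participant | 1.12 | 1.41 | 2.23 |
| A | Coverage of the nominal 90% CI | 93.5% | 97.9% | 99.9% |
| B | Width ratio, unpaired/paired | 1.15 | 1.55 | 2.58 |
| B | Coverage of the nominal 90% CI | 94.4% | 98.8% | over 99.9% |

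At ICC 0.1 the factor under A is 1.05, and at ICC 0 there is no loss. With the participant term (A) or pairing (B), coverage is about 90% throughout.

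**Reading C: one extreme per study.** Only here is the stated reason literally true. The extreme over four periods is assigned to the period and treatment that produced it, and period plus treatment is fitted to 28 values (8,000 trials per setting, with 5 to 13 rank-deficient trials left out of each). The outcome now selects the treatment, so the two groups are no longer a randomised comparison.

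| True difference (within-participant SD) | Quantity | ICC 0.2 | ICC 0.5 | ICC 0.8 |
|---|---|---|---|---|
| 0 | Coverage | 89.9% | 89.8% | 90.3% |
| 0.2 | Mean estimate | 0.059 | 0.064 | 0.064 |
| 0.2 | Coverage | 87.4% | 89.0% | 89.7% |
| 0.5 | Mean estimate | 0.165 | 0.170 | 0.152 |
| 0.5 | Coverage | 77.7% | 84.0% | 88.2% |

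Maxima were simulated. By symmetry, the minimum for potassium behaves the same way.

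**The case against.** The sponsor ties the change to the PD derivation. That derivation is not visible and may lie in redacted parts of the SAP (6.2.3, 6.2.6 and what follows, or 4.8 on changes to protocol-defined analyses). Redacted text is not missing text, so the mismatch is shown against the sampling schedule rather than against the derived variable. The consequence also depends on which reading applies. No passage describes reading C, and reading B cannot carry the period term that SAP 4.4 states. Every magnitude rests on an assumed ICC, and the 28 is the PK-set target while PD uses the FAS. The endpoints are exploratory with no visible decision rule. Under A with complete data the ratio is unchanged and the error is conservative.

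Most of this stands as a limit on size. It does not rescue the model. Single observation may simply mean one derived value per period, but that is reading A, with four correlated values per person. Of the derivations considered, A and B make the comparison inefficient and C attenuates it. A residual within-participant covariance could replace the random effect under A or B, but SAP 4.4 states none. The choice of 28 hardly affects the width ratios.

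**Conclusion.** The concern holds. The current SAP and protocol specify different PD models, and the reason given for the difference does not fit a design with four dosing and measurement days per participant. With one value per period, the 90% CI is too wide by 1.05 to 2.23 times for ICC 0.1 to 0.8. With one extreme per treatment, it is too wide by 1.15 to 2.58 times for ICC 0.2 to 0.8. With one extreme per study, a true difference is estimated at roughly a third of its size, although coverage is nominal when there is no difference. These readings may not be exhaustive, and all figures rest on assumed ICCs.

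This should be fixed but does not threaten the main results. The endpoints are exploratory, the change is disclosed, the PK models keep the participant effect, and the descriptive potassium, heart-rate and QTc summaries are unaffected. If periods are missing, the ratio without a participant term would also mix in between-participant differences.

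**What to change.** In SAP 4.4, state that one value of each PD endpoint is derived per participant per period. Restore participant as a random effect alongside period and treatment, as protocol 9.3.2.1 specifies. Add a version-history entry that corrects the single-observation reason.

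The cost is SAP wording, one version-history entry and one model term in the code. If the existing derivation gives fewer than one value per period, the derivation code must change as well. No extra data are needed, because potassium and ECG are already scheduled on every dosing day.

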## 4.5. Safety Analyses

Safety analysis set will be used for the analysis of safety endpoints. Secondary safety estimand to analyses safety endpoints (refer Section 4.3.1.1.) will be implemented for Cohort 1 and Cohort 2. Safety analysis will be summarized by study treatment.

Details of the planned displays for safety data are provided in Output programming specifications (OPS) and will be based on GSK Data Standards and statistical principles.

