- c. **Physical examination:** Complete physical examinations will be conducted at screening. Symptom driven physical examinations are conducted at discharge/early withdrawal and may be conducted at any other time, per investigator discretion.
- d. **Pregnancy testing:** Female participants will be required to take a serum pregnancy test (Day-1, Screening and Discharge/Early Withdrawal).
- e. **SARS-CoV-2 PCR testing:** Sampling of nasal and throat mucosal cells for PCR testing for SARS-CoV-2 may be performed at the discretion of the site based on local guidelines.
- f. **Clinical laboratory assessments:** Including clinical chemistry [includes liver chemistries], hematology, and urinalysis will be conducted at screening, on Day-1 (admission), and at discharge.
- g. **Blood sampling for serum potassium (PD) and glucose (safety):** On each dosing day (Day 1, 4, 7 and 10), blood samples will be taken predose at: 15 and 30 minutes and 1, 1.5, 2 and 4 hours postdose.
- h. **Vital signs:** Systolic and diastolic blood pressure, and PR) vital signs will be recorded at screening, admission, on each dosing day (Day 1, 4, 7 and 10) at predose and at the following time points postdose: 15, 30 minutes, 1, 2, 4 hours and at discharge. Assessed after a minimum of 5 minutes of the participant resting in the supine position with a completely automated device.
- i. **12-lead ECG:** 12-lead ECG will be recorded at screening, admission, on each dosing day (Day 1, 4, 7 and 10) at predose and at: 30 minutes postdose and at discharge. As the ECG parameters QTc and HR will be PD parameters, ECG will be measured in triplicate at predose on Days 1, 4, 7 and 10. The 3 predose measures will be recorded in the eCRF and will be averaged for QTc interval and HR to derive 1 baseline value which will be recorded in the eCRF. Each individual capture of the triplicate 12-lead ECG set should be obtained as closely as possible in succession, but no more than 5 minutes apart from first to third ECG. Postdose 12-lead ECG measurements will be single measurements on all dosing days. Discharge or early discontinuation 12-lead ECG measurements will be single measurements. **Note.** if an ECG meets potential stopping criteria, then the ECG measurement should be repeated in triplicate, with the averaged QT and QTcF used to determine stopping.

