Descriptive statistics (n, mean, standard deviation (SD), median, minimum value (min), and maximum value (max)) will be presented for quantitative measurements of absolute value for continuous laboratory parameters (clinical chemistry and hematology) including serum potassium and glucose at baseline and each assessed visit as per SOA of protocol in on-treatment period for Safety analysis set. Counts and percentages will be produced for qualitative measurements measure laboratory parameters for on-treatment period for Safety analysis set.

As per protocol SOA Section 1.3, safety laboratory parameters data are not collected for follow up visit, therefore on-treatment period will be same as overall period.

Summary of liver monitoring/stopping event will be summarized by counts and percentages. Refer to protocol Appendix 5, Section 10.5 Liver safety for more description of liver events.

Participants listing of all clinical laboratory data will be produced for each treatment and period in Safety analysis set.

If a laboratory value which is expected to have a numeric value for summary purposes, has a non-detectable level reported in the database, where the numeric value is missing, but typically a character value starting with ‘<=’ or ‘=>’ (or indicated as less than x or greater than x in the comment field) is present, the number of significant digits in the observed values will be used to determine how much to add or subtract in order to impute the corresponding numeric value.

- Example 1: 2 significant digits = ‘<= x’ becomes  $x - 0.01$
- Example 2: 1 significant digit = ‘=> x’ becomes  $x + 0.1$
- Example 3: 0 significant digits = ‘<=x’ becomes  $x - 1$

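### Discharge laboratory panels, vital signs and ECG follow two test and two reference doses in every completer, so the SAP's by-treatment rule for safety summaries does not fit them

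*SAP*

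**What the plan says.** SAP 4.5 opens its safety section with a rule that carries no exception: "Safety analysis will be summarized by study treatment". It then leaves display details to the output programming specifications, which are not among the documents.

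Footnote f of the schedule of activities (Protocol 1.3) gives the laboratory timing: "Including clinical chemistry [includes liver chemistries], hematology, and urinalysis will be conducted at screening, on Day-1 (admission), and at discharge". No such panel is scheduled between doses. Footnotes h and i put vital signs and ECG on each dosing day and also at discharge.

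Protocol 4.1 gives the sequences, "Treatment Sequence 1: TRRT" and "Treatment Sequence 2: RTTR", "with 15 randomized to each treatment sequence" in each cohort. It places "dosing on Day 1, Day 4, Day 7, and Day 10. Participants will be discharged on Day 11".

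In the text after Table 6, SAP 4.5.3.1 summarizes absolute laboratory values "at baseline and each assessed visit as per SOA of protocol in on-treatment period". It makes no exception for discharge and lists all laboratory data by treatment and period. SAP 4.1.2 (Table 2) takes Day -1, before any dose, as the laboratory baseline. The only rule in the SAP's safety sections for attributing an observation to a product's period is the one for adverse events in SAP 4.5.2. SAP 6.1.2, by contrast, tabulates demographics by sequence and overall.

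**The concern.** A by-treatment table makes sense in a crossover when each participant contributes a value under each product. Dosing-day potassium, glucose, vital signs and ECG meet that condition. The discharge assessments do not: there is one value per participant, taken after both products have been given twice.

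Absolute laboratory values are a named secondary safety endpoint (Protocol 3, Table 3). If the stated rule is applied to the discharge panel, a reader of the study report could take two similar columns as evidence that the propellants do not differ in their laboratory effects. The columns would hold either two sequence groups with equal cumulative exposure or the same people twice.

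**Working it through.** The plan gives no figure on this point, so the check is mainly structural.

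**Inputs.** Doses on Days 1, 4, 7 and 10, discharge on Day 11, sequences TRRT and RTTR, and 15 randomized to each per cohort (Protocol 4.1). One post-dose laboratory panel, at discharge (Protocol 1.3, footnote f).

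**Step 1: exposure at discharge.** For a completer:

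| Sequence | Test doses | Reference doses | Last product | Days from each test dose to Day 11 |
|---|---|---|---|---|
| TRRT | 2 | 2 | T | 10 and 1 |
| RTTR | 2 | 2 | R | 7 and 4 |

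**Step 2: possible by-treatment layouts.**
- Labelled by last product, the test column is exactly the 15 TRRT participants and the reference column exactly the 15 RTTR participants. Product label and sequence are completely aliased.
- Labelled by products received, all 30 participants appear in both columns, which are then identical if all complete.

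The Day -1 value precedes all dosing and belongs to neither product.

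**Step 3: what the last-product columns could show.** The documents give no time course for any laboratory effect, so I assume one. Let each test dose add an effect relative to reference, let effects add across doses, and let a fraction r remain after each 3-day interval. Take the part of the last dose's effect still present at discharge as 1 unit.
- TRRT carries 1 + r³ (doses 4 and 1).
- RTTR carries r + r² (doses 3 and 2).
- Expected difference = 1 + r³ − r − r² = (1 − r)²(1 + r).

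| r | TRRT | RTTR | Difference |
|---|---|---|---|
| 0 | 1 | 0 | 1 |
| 0.5 | 1.125 | 0.75 | 0.375 |
| 0.8 | 1.512 | 1.44 | 0.072 |
| 1 | 2 | 2 | 0 |

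The difference shrinks as the effect becomes more persistent, and vanishes only if nothing decays. A delayed effect can even point the wrong way: one present only from 3 to 8 days after a test dose would reach Day 11 in RTTR alone (7 and 4 days) and so appear under the reference heading.

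**Step 4: do the period definitions settle the label?** SAP 6.2.2 ends Period 4 strictly before one day after its dose start, while Protocol 1.3 (footnote a) places the end of confinement at roughly 24 hours after the last dose. A discharge sample can therefore count as on-treatment by date and still fall inside or outside Period 4, depending on the hour.

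**Step 5: data the rule does fit.** Dosing-day measurements give up to 30 × 2 = 60 participant-periods per product per cohort.

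**The case against.** The strongest reply is that no mislabelled table is documented. SAP 4.5.3.1 names no columns for the discharge panel, nothing assigns a discharge value to the last product, and the programming specifications may handle this well. It is therefore right not to say that the tables will be wrong. What remains is a general rule without exception, from which specifications written to the SAP would start and which does not fit these data.

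A reader might infer that a persistent test effect of any size gives zero difference between the columns. The documents do not support that. Zero requires an additive effect that does not decay before Day 11. With half remaining per interval, 0.375 of the last-dose effect would still show. The last-product contrast is confounded with sequence, but it is not empty.

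A reader might also infer that by-sequence tables would reveal what by-treatment tables hide. They would not. They hold the same participants as the last-product columns under correct names. The limit comes from having no panel between periods, which no table layout can repair.

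Nor does equal exposure hold for every participant. The discharge assessments also serve early discontinuation, where test and reference doses may be unequal.

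Finally, the consequence is limited, and this stands. The safety estimand asks for mean absolute values, with no test-versus-reference contrast, interval or test. The laboratory risks named in Protocol 2.3.1, hypokalemia and hyperglycemia, are measured in every period. Liver events are counted separately, and clinically significant laboratory changes are recorded as adverse events, which have a period rule.

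**Conclusion.** The point holds for the discharge assessments: hematology, chemistry, urinalysis, vital signs and ECG. Applied as written, the by-treatment rule gives either two sequences under product headings, about 15 per column per cohort before dropout, or near-duplicate columns. In the first layout last product is confounded with sequence, and an additive effect that does not decay cancels. Smaller differences from partly persistent effects rest on the assumed decay pattern, which the documents neither give nor exclude.

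The conclusion assumes completers and takes the SAP's rule at face value, since the programming specifications cannot be seen. The tables are descriptive, dosing-day safety data are unaffected, and so is the primary PK analysis. The correction is worth making because it prevents a misreading at little cost, not because it changes any inference in the study.

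**What to change.** In SAP 4.5.3, add an exception to the by-treatment rule:

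- Present Day -1 and discharge hematology, chemistry and urinalysis, and discharge vital signs and ECG, by sequence and overall within cohort.
- State that these displays do not support a test-versus-reference comparison.
- Keep by-treatment summaries only for assessments made within each period: dosing-day potassium, glucose, vital signs and ECG.

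Change from Day -1 for the laboratory panels is optional. The stated endpoint is the absolute value, but a pooled pre/post view may be useful and the baseline is already defined.

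The cost is SAP wording and table shells, with no new data or visits. The sequence-plus-total layout is already specified for demographics in SAP 6.1.2. The gain is correct labelling and a pooled column; a product contrast at discharge is not recovered.
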